In terms of monetary expenditures, one tube of octyl-2-cyanoacrylate costs approximately \$24. Macario et al site that one minute of operating room time costs approximately \$29, varying in case complexity. We would like to assess the total costs between the two techniques when time in the OR is taken into account.

We hypothesize that the scars will be equivalent in assessment and ultimately be less costly with less patient distress. We also suspect that the skin glue may create an occlusive barrier to infectious contamination of the wounds and potentially a lower complication rate.

Objectives

List your research objectives. Please include a summary of intended research objectives in the box below.

- 1. To determine if octyl-2-cyanoacrylate provides equivalent wound healing compared to conventional non-absorbable skin suture techniques
- 2. To determine if octyl-2-cyanoacrylate provides equivalent scar appearance compared to conventional non-absorbable suture techniques
- 3. To determine the cost effectiveness of the use of octyl-2-cyanoacrylate for skin closure compared to conventional non-absorbable suture techniques
- 4. To determine if octyl-2-cyanoacrylate results in equivalent complication rates compared to conventional non-absorbable suture techniques

Study Design

Describe and explain the study design (e.g., observational, secondary analysis, single/double blind, parallel, crossover, deception, etc.).

- · Clinical Research: Indicate whether subjects will be randomized and whether subjects will receive any placebo.
- Community-Based Participatory Research: If you are conducting community-based participatory research (CBPR), describe
 strategies for involvement of community members in the design and implementation of the study, and dissemination of results from
 the study.
- Qualitative research: Indicate ranges where flexibility is needed, if a fixed interview transcript is not available, describe interview
 topics including the most sensitive potential questions.

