Research Repositories: If the purpose of this submission is to establish a Research Repository (bank, registryou plan to collect is already available from a commercial supplier, clinical lab, or established IRB approved research repository, provide scientific justification for establishing an additional repository collecting duplicate material. Describe the repository design and operating procedures. For relevant information to include, see the UK Research Biospecimen Bank Guidance or the UK Research Registry Guidance.

The proposed study is a two staged prospective study comparing skin closure with octyl-2-cyanoacrylate (Dermabond) with conventional non-absorbable sutures in the direct excision brow lift.

In stage 1, subjects will be consented to receive one of two surgical closing techniques on a bilateral brow ptosis repair: 1) deep dermal sutures and superficial interrupted sutures (the standard of care at the University of Kentucky); or 2) deep dermal sutures and octyl-2-cyanoacrylate skin glue application for superficial closing. Subjects will undergo a single closing technique on both sides. Four subjects will complete surgery in each arm (n=8 subjects total: n=4 for arm 1, and n=4 for arm 2). After the follow-up period, the scar appearance between groups will be compared. If there the octyl-2-cyanoacrylate (dermabond) group have worse appearing scars, then we will not continue to study. If the difference in appearance is negligible, then we will return to the IRB for approval to advance to stage two.

Stage two is outlined below:

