- If you will conduct a record or chart review, list the beginning and end dates of the records you will view.

See attachments for the POSAS survey that will be used to grade scar appearance.

Attachments

Attach Type File Name			
DataCollection 77074_DataCollection_267377.pdf			
DataCollection dss_2017_12_22_patel_ds-00686-2016_sdc1.pdf			

Resources

Describe the availability of the resources and adequacy of the facilities that you will use to perform the research. Such resources may include:

- Staffing and personnel, in terms of availability, number, expertise, and experience;
- Computer or other technological resources, mobile or otherwise, required or created during the conduct of the research;
- Psychological, social, or medical services, including equipment needed to protect subjects, medical monitoring, ancillary care, or counseling or social support services that may be required because of research participation;
- Resources for communication with subjects, such as language translation/interpretation services.

Patient histories, physical examinations, and discussions regarding candidacy for the study will occur in the University of Kentucky Ophthalmology Clinics. The operations will be performed at the University of Kentucky Center for Advanced Surgery. The equipment used to perform the procedure will be in accordance with the usual standard of care for a direct excision brow lift. [name] and the enrolled patient will fill out the described questionnaires. We do not anticipate the need for psychological or social services. We do not anticipate the need for special medical monitoring, ancillary care, equipment needed to protect subject other the usual standards in perioperative and intraoperative care.

Potential Risks & Benefits

Risks

- Describe any potential risks including physical, psychological, social, legal, ability to re-identify subjects, or other risks. Assess
 the seriousness and likelihood of each risk.
- Which risks may affect a subject's willingness to participate in the study?
- · Describe likely adverse effects of drugs, biologics, devices or procedures participants may encounter while in the study.
- Qualitative research describe ethical issues that could arise while conducting research in the field and strategies you may use to handle those situations.
- Describe any steps to mitigate these risks.

Benefits

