Hi, this question does not apply to our study. There were no results to communicate as there were no tests that were done. This was purely an observational study with a survey that the patient filled out in their postop appointment. I am not sure what the violation is that is being alleged here

Protocol Type Comment by [name] - ORI to IRB/PI on 6/4/2024 3:03:53 PM

Both of the uploaded signed consents are missing checkboxes and initials in the paragraph re: permission to contact participants for return of results or incidental findings (p. 4.). Please submit a violation report for this issue and include the following: 1) Was this missed on all of the signed consents? and 2) Do you anticipate any issues arising from missing this selection? (i.e., how likely is it that there were any incidental findings or results to be returned?) Let me know if you have questions about this request.

Date: March 30, 2025

Identifiers: NCT05981443 Unique Protocol ID: BrowPtosis

Brief An Analysis of Dermabond vs. Non-Absorbable Sutures in Skin Closure for

Title: Brow Ptosis Procedures

Our statistical analysis plan for this pilot study consists of using only data gathered using the POSAS survey administered to patients at their post-operative visits. We used this survey and demographic data to perform basic descriptive statistics to detect if there was a difference between the reported rates of patient satisfaction and ratings of their scars.

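### The SAP's only comparison sentence names no closure arm, POSAS score or visit, leaves the satisfaction rate undefined, and plans no between-arm estimate or interval

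*Combined protocol and SAP*

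**What the plan says.** The SAP, dated March 30, 2025, is two sentences under a header that carries the study title.

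- Data: "using only data gathered using the POSAS survey administered to patients at their post-operative visits".
- Method: "We used this survey and demographic data to perform basic descriptive statistics".
- Purpose: to "detect if there was a difference between the reported rates of patient satisfaction and ratings of their scars".

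Neither sentence contains the words Dermabond, suture, arm or group. The two closures appear only in the title above: "An Analysis of Dermabond vs. Non-Absorbable Sutures in Skin Closure for".

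The protocol is clearer about the question. Objective 2 reads "To determine if octyl-2-cyanoacrylate provides equivalent scar appearance compared to conventional non-absorbable suture techniques". For stage 1, the Study Design section plans "n=8 subjects total: n=4 for arm 1, and n=4 for arm 2" and says: "After the follow-up period, the scar appearance between groups will be compared". The Data Collection & Research Materials section gives the instrument: "See attachments for the POSAS survey that will be used to grade scar appearance". The Research Procedures section says that patients are randomised to one closure, used on both brows.

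**The concern.** A SAP should let a second analyst reproduce the comparison from the text. Here the one sentence that states a comparison puts satisfaction rates beside scar ratings and leaves out the treatment contrast. It also leaves open which POSAS score is meant, which post-operative visit supplies it, whether the unit is the patient or the brow, and what summary of the arm difference is shown.

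This matters beyond tidiness. The stage 1 result is meant to decide whether the investigators ask the IRB to move to stage two: worse scars with glue stop the study, and a negligible difference allows the request. Objective 2 is worded as equivalence, and the documents give no margin. If the only output is descriptive, with no arm difference and no interval, a reader may take two similar-looking summaries as evidence that the closures are equivalent.

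**Working it through.** There is no figure in the SAP to reproduce. The check is a comparison of texts, followed by one calculation to show scale.

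**Step 1: what each place supplies.**

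| Element | SAP sentences | Elsewhere in the documents |
|---|---|---|
| Arms compared | not named | SAP header (title); Study Design, stage 1 |
| Outcome | satisfaction rates; scar ratings | scar appearance (Objectives; Study Design) |
| Instrument | POSAS completed by patients | POSAS, for grading scar appearance (Data Collection); patient and observer both score (Study Design, stage two outline) |
| Score or item used | not named | not named; the form is an attachment that is not shown |
| Rule for a satisfaction rate | none | none |
| Visit | post-operative visits, unspecified | 10 days and 3 months (Study Design, stage two outline); the week after surgery and six weeks (Data and Safety Monitoring) |
| Unit | not stated | one closure on both brows of each patient (Study Design, stage 1) |
| Between-arm estimate or interval | none | none |

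The contrast can be recovered from elsewhere. The score, visit, satisfaction rule and summary cannot.

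**Step 2: the satisfaction rate.** POSAS is the SAP's only outcome source, so a satisfaction rate has to come from POSAS, either from an item already on the form or by a rule applied to a score. Neither is identified.

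**Step 3: the unit.** In stage 1 both brows of a patient receive the same closure. Seven patients give up to 7 × 2 = 14 brows, but only seven independent units. If brows were scored separately, they should be averaged within the patient.

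**Step 4: how wide an honest interval would be.** The continuing-review form, under Subject Info To-Date, gives 7 enrolled and no split by arm. I assume that all seven have a score at the chosen visit, that the SD is common to both arms, and that the interval is two-sided 95%. Splits of 4 v 3 and 5 v 2 are assumptions; 4 v 4 is the plan. For arms of size a and b:

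half-width = t(0.975, a + b − 2) × SD × √(1/a + 1/b)

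- 4 v 4: 2.447 × √(0.250 + 0.250) = 2.447 × 0.707 = 1.73 SD
- 4 v 3: 2.571 × √(0.250 + 0.333) = 2.571 × 0.764 = 1.96 SD
- 5 v 2: 2.571 × √(0.200 + 0.500) = 2.571 × 0.837 = 2.15 SD

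Even with an observed difference of exactly zero, the interval at 4 v 3 would run from −1.96 to +1.96 SD. These figures do not prove the wording defect, which rests on Steps 1 and 2. They show why the result should be reported with an interval and why similarity must not be read as equivalence.

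**The case against.** The strongest reply is that this is grammar, not design. The natural reading of the sentence is a difference in two outcomes, satisfaction and scar ratings, with the groups left implicit. The title directly above names both closures, and the Study Design section states the between-group comparison in plain terms. The SAP also calls the study a pilot, for which descriptive statistics are a reasonable choice. Finally, any replacement written now is itself specified after the data.

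Most of this stands. Glue versus suture is the likely intent, and a reader who inferred that the trial never compares the closures would go further than the documents allow. A descriptive approach is also defensible with seven patients, but an arm difference with an interval is an estimate rather than a test and fits that approach. The reply does not supply the score, visit, satisfaction rule or summary, none of which the documents give.

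Three further inferences are tempting and not supported:

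- **That a scar score is turned into a rate.** The SAP keeps scars as ratings; the word rates is attached to satisfaction.
- **That a cut-point was picked after the data were seen.** The SAP is in the past tense and postdates closure, but no cut-point is mentioned, and the unseen form may hold a satisfaction item that needs none.
- **That most of the information is thrown away.** The scar ratings are still summarised, and nothing in the documents allows such a loss to be measured.

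Significance tests on a satisfaction rate would not help either. The SAP plans no test, and the split by arm is not reported.

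**Conclusion.** The concern holds as a fault of specification. The SAP's only comparison sentence omits the treatment contrast, defines no satisfaction rate, names neither POSAS score nor visit, and plans no between-arm estimate or interval. The documents do not show that a different question was analysed or that a favourable rule was chosen.

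The fault should be corrected because the missing result is the one that objective 2 and the stage-two decision depend on. As for size, the arm difference would carry a half-width of about 2.0 to 2.2 SD for seven patients at the splits considered. That rests on the assumed splits, complete scores and a common SD. On those assumptions the data can exclude only very large differences.

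**What to change.** Replace the comparison sentence with:

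> For each randomised closure arm, list every patient's POSAS patient-scale score at each post-operative visit, with the patient as the unit (averaging the two brows if they were scored separately), and report the Dermabond minus suture difference in arm means with a 95% CI at one named visit; a CI that includes zero will not be read as equivalence.

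Then:

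- Say which patient-scale score is used.
- Name the visit only after the follow-up times in Study Design (10 days and 3 months, in the stage two outline) and Data and Safety Monitoring (the week after surgery and six weeks) have been reconciled.
- If the form has a satisfaction item, identify it and report it by arm on its original scale. Otherwise drop the satisfaction rate.
- State that this analysis was specified after data collection. The IRB form marks all study activities complete, and the SAP is dated March 2025.

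The cost is a few sentences and a short table from data that should already be in hand. The downside is that the interval will be very wide and the report will have to say so.
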